Task 1.2.	Selection of valid and reliable instrument to assess pain and the relevant clinical domains identified in the previous phase.												
Task 1.3.	Transfer of chosen instruments into a digital format to be applied through an electronic application to facilitate data collection and codification.												
Task 1.4.	Contact with technology companies and acquisition of portable tES equipment, actigraphy devices and stimulators for quantitative sensory testing.												
Task 1.5.	Review of the literature and definition of quantitative sensory tests (CPM/TSSP) and EEG protocols.												
Task 1.6.	Preparing of application and obtaining the Ethical Committee approval												
Task 1.7.	Familiarization of researchers with purchased devices and conducting pilot tests to ensure their correct performance/operation.												
WP2. Recruitment and first evaluation of chronic refractory pain patients: Pre-treatment phase													
Task 2.1.	First contact and recruitment of participants by physicians from Public Health System.												
Task 2.2.	Telephone contact with participants to explain the nature of the project and arrange a face-to-face assessment session.												

WP5. Statistical analyses of the clinical trial data, discussion of results and writing of reports													
Task 5.1.	Data analysis of pre-treatment evaluation results: Pain processing and modulation indexes (CPM, TSSP, EEG) and correlations with clinical features of patients.												
Task 5.2.	Data analyses of immediate tES effects/outcomes and potential predictors of treatment efficacy.												
Task 5.3.	Data analyses of long-term tES effects/outcomes.												
Task 5.4.	Group discussions about the available results.												
Task 5.5.	Writing reports and dissemination of results for scientific community.												

9. Security and ethical-legal issues

We are committed to adhere to all relevant international, EU and national legislation and guidelines relating to the conduct of clinical studies. Since our research involves human samples, we will organize a preliminary seminar on ethics questions to guarantee respect for research participants and the appropriate behaviour of the involved researchers and clinicians in regard to the health and welfare of the participants.

The purchased transcranial electrical stimulation devices have obtained the CE Certificate for research use, and in some countries, for clinical use as an off-label treatment. This certificate warrants the compliance with European standards about the security offered by the equipment.

For research, in most countries, only IRB/Ethical Committee approval is required, since the studies using tDCS are considered to be of minimum risk, provided that the exclusion criteria are strictly applied (i.e., intracranial ferromagnetic devices or implanted stimulators; antecedents of, or active epilepsy; history of neurosurgery, traumatic brain injury with loss of consciousness, and/or cortical lesion). Researchers are committed with ascertaining that every single enrolled patient complies with all the inclusion criteria and he/she does not match the exclusion criteria, in order to ensure that there is no health condition or circumstance which advises against participating in the study.

As explained above, no significant adverse events have been reported by a comprehensive review covering more than 18.000 stimulation sessions and approximately 8.000 patients (Antal et al., 2017). Thus, at present, most IRB committees approve tDCS treatments based on the promising data already available, without major concerns or obstacles. At the time of uploading this document, we have already obtained the approval from the competent Ethical Committee (Research Ethical Committee of Santiago-Lugo; Registry Code: 2021/021).

This project is developed following the requirements of Helsinki Declaration (1964) and subsequent assembly ratifications (Tokyo, 1975; Venezia, 1983; Hong Kong, 1989; West Somerset, 1996; Scotland, 2000; Seoul, 2006; Fortaleza, 2013) about the ethical principles for medical investigations involving human beings; as well as the national-scope guidelines collected in the RD 1090/2015, about clinical trials and medical praxis.

As in any other randomized clinical trials, a percentage of participants will be assigned to a Sham condition. Patients will be aware about this fact before the start of the study although, as for the researchers, patients will not know which was their treatment group until the end of the trial. Given that participants will be randomly assigned to one of the groups, we guarantee that there is no discrimination based on gender, race, sexual orientation or any other individual characteristic. Besides, patients in the placebo group will continue to receive their regular treatment and, in addition, due to their participation in the study, will receive day-to-day attention on their health state evolution.

As far as the data processing is concerned, researchers will not ask for personal information which could reveal the identity of the patients, thus maintaining anonymity. We are committed to respect the European and national legislation about Personal Data Protection, whose highest authorities refers to the *Regulation (EU) 2016/679 of the European Parliament and of the Council, of 27 April 2016, on the Processing and Protection of Personal Data* and the Spanish law called *Ley Orgánica 3/2018, de 5 de diciembre, de Protección de Datos Personales y garantías de los derechos digitales*.

The research centre is responsible for the data treatment and processing. Data collected will be exclusively used for the objectives described in this investigation protocol and maintained during the strictly necessary time to purchase those objectives. The nature and objectives of the research will be perfectly explained and clarified to the participants and they will have to sign an informed consent before their enrolment.

Each participant will be assigned with a code at the beginning of the study which does not allow to discover their identity. These codes will be current during the whole trial, thus patients will introduce it in questionnaires and daily surveys instead of any other personal data, such as name or surname. Therefore, data collected from participants will be saved in a password-protected file which will not contain any identifying information. During the data analyses phase, researchers will just have access to the participant code, without knowing the identity of the data which they are working it.

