One of these techniques for brain stimulation is the **transcranial Electrical Stimulation (tES)**. By applying a low current over the motor cortex through the scalp, this technique can excite or inhibit the neural activity, thus modulating brain processes like pain perception (Nitsche & Paulus, 2000; Nitsche et al., 2008). The most frequently used tES technique is **transcranial Direct Current Stimulation (tDCS)**. It consists of the application of a constant low-intensity current (1-2 mA) usually through 2 electrodes (anode and cathode) placed on the scalp. This stimulation induces relatively sustained changes in cortical excitability and neuroplasticity (Paulus, 2003). More recently, **transcranial Alternating Current Stimulation (tACS)** has been used to modify cortical functioning (Fröhlich et al., 2015).

Transcranial electrical stimulation may be a key component for correcting defective central pain generating mechanisms. tDCS has been suggested to induce anti-nociceptive effects on experimental pain and have pain-relieving effect in different clinical conditions, using anodal stimulation over the precentral region contralateral to pain (Santos-Portilla et al., 2013). Although different cortical brain targets have been tested, the stimulation of primary motor cortex (M1) appears the most effective cortical target in chronic pain patients and their clinical improvements last beyond the time stimulation, probably due to solid neuroplastic modifications (Lima & Fregni, 2008). This finding is consistent with the hypothesis that cortical networks play a key role in pain processing and that the primary motor cortex (M1) may be a gateway to deep pain-related networks such as the thalamic nuclei and the cingulate gyrus (Baliki et al., 2008; Maarrawi et al., 2007). Evidence for pain reduction through M1 tDCS has been reported for chronic pain manifestations as diverse as pelvic pain, spinal cord pain, cancer, diabetic neuropathy, low-back pain, temporomandibular disorders, and migraine, among others (Lefaucheur, 2016).

Transcranial electric stimulation (tES) has several advantages: it is portable, non-invasive, engineered from low-cost components, has minimal adverse effects, is well

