Identified caregivers are invited to a brief face-to-face interview to evaluate their burden and health status. Given the exploratory character of this purpose, we do not set a priori sample size for caregivers, although the question about the caregiver will be formulated to all the patients.

5. Description of the treatment

Home-based transcranial electrical stimulation device consists of a custom headgear with fixed electrode sites and built-in cabling made for a simplistic setup for tDCS/tACS stimulation. Systems are equipped with strict dose control feature that provide reliable control over the intensity and timing of stimulation, turning these devices into a feasible and safe clinical alternative.

The equipment is specifically designed for easy and simplistic self-setup and allows the researchers to remotely check the position of electrodes and also monitor the stimulation session. This is possible because the devices have an Internet wireless connection and send the data obtained to an online platform, only accessible to the principal researchers.

From pre-stimulation set-up, to during stimulation monitoring, to post-stimulation confirmation, the device provides an intuitive and clear indication of electrode contact quality, facilitating the proper adjustments to ensure a successful stimulation. In case stimulation is aborted or interrupted, impedance is abnormal, or other faults are detected, the system will automatically abort or alter stimulation and the incident details stored. This system also allows researchers to supervise the treatment compliance.

¹ It must not be overlooked that patients with chronic pain can find difficulties/limitations to accomplish the basic daily tasks and thereby be partially dependant (Meulders, 2019; Zale et al., 2013)

Besides, these devices use a software which allows a double-blinded procedure. Neither the researchers nor the participants will know what kind of stimulation is receiving each of them.

The intervention plan comprises fifteen stimulation sessions applied with a daily frequency during an uninterrupted period of time which covers just over two weeks. Thus, sessions will be scheduled for each patient before the beginning of the treatment, arranging with the patient the hour frame for stimulation. Stimulation parameters/sites for each condition will be as follows:

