- Transcranial direct current stimulation (tDCS). Current intensity of 2mA applied during 20 minutes at the left M1, with anodal electrode placed in C3 and cathodal in FP2, following the International 10-20 EEG System. Ramp-up and ramp-down comprises 15 seconds at the beginning and end of the stimulation period.
- Transcranial alternating current stimulation (tACS). Following the design established by previous studies (Ahn et al., 2019), two electrodes will be placed at F3 and F4 and connected together for 10-Hz tACS (or the frequency which shows best sensitivity or specific), and one electrode at Pz will be the return electrode. This setting is used to stimulate the somatosensory cortical region. Stimulation will last for 20 minutes, with a ramp-up and ramp-down of 15 seconds at the beginning and end of the session.
- Sham stimulation. The electrode montage will be either the tDCS (for half of the participants) or the tACS montage (for the other half), and we will just apply the current at the ramps terms, but no current in the interval between the ramps which practically comprises the whole session.

At the second pre-treatment evaluation session, patients will receive the portable stimulator with the proper explanations about its functioning. It is planned to make a training stimulation session during this visit to ensure that patients are able to connect and manage the device.

6. Evaluation protocol and follow-up

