6.1. Evaluation phases

Regarding the evaluation protocol, pre-treatment assessment is divided in two different sessions, separated by two weeks.

After obtaining their contact number from physicians, researchers maintain a first phone talk with the proposed participants to ensure they not comply with any exclusion criterion. During this brief interview, the first meeting with patients is also scheduled, according to their availability.

The first face-to-face session is intended to initiate the pre-evaluation process and it takes place fifteen days before starting the treatment. After signing the informed consent, participants will complete an exhaustive assessment protocol which includes an interview about their health status and clinical history, a set of quantitative sensory tests (Pain thresholds, CPM, TSSP) and some other questionnaires to assess psychosocial variables.

From this point to the end of the post-treatment evaluation, patients are required to complete a daily online survey about their symptoms and health condition. Moreover, patients will be given a wristband actigraph which should wear during the whole research period (except follow-up), in order to monitor their physical activity and sleep patterns.

The next evaluation will take place two weeks after the first one. During this period, participants are required to complete a daily online survey about their symptoms and health condition. Moreover, they are given a wristband actigraph which allows to monitor their physical activity and sleep patterns.

At the second session, patients will complete electroencephalographic records in different conditions and tasks, some of which include painful stimuli. Furthermore, we will collect additional clinical features through validated questionnaires and may also repeat the quantitative sensory testing. Caregivers of chronic pain patients will also be invited to this appointment to maintain an interview with researchers, which aims to determine their health status and the stress-related to the caring tasks.

Finally, researchers will give the participants the portable stimulator to apply the tDCS/tACS treatment, with the properly explanations about its functioning. It is planned to make a training stimulation session during this visit to ensure that patients are able to

connect and manage the device; researchers will also be available to make a video-call to assist the participant in the first stimulation session.

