After completing the treatment period, participants are summoned to other two evaluation sessions with the same structure and assessment tools as in pre-treatment phase; in case of the daily measurements, the comparison is made between the average of the pre-treatment period and that of the post-treatment period. Therefore, differences observed between these two time-measurements are considered as index of the treatment efficacy. At the post-evaluation session, participants will also answer some questions about the satisfaction with the treatment and self-perceived usefulness/improvement.

Finally, in order to assess the long-term improvement derived from tES, we will contact participants by phone in order to invite them to a follow-up session six months after finishing the treatment. All questionnaires and sensory tests will be applied in the same way, except for daily numerical rating scale. Differences between these results and those obtained in pre-evaluation and post-evaluation will be analysed.

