Finally, we will explain the daily assessment plan to patients, which starts at this point (i.e., fifteen days before the treatment onset) and continues until fifteen days after the stimulation sessions have finished. Every day during this period, participants will be requested to complete a brief online survey to track the intensity of their symptoms and obtain a more reliable measure. These questionnaires will be sent to patients by phone message, after getting permission from participants.

Specifically, the daily survey consists of several Numerical Rating Scales (NRS) of eleven points (0-10) which ask about the intensity and unpleasantness of pain, interference, fatigue and medication usage, among others. During treatment period, participants can also report any side effect of stimulation through these questionnaires. For each symptom, we will obtain an average of measures obtained before starting the treatment, other average with measures during the treatment and one last average for post-treatment phase (e.g., fifteen days after finishing the intervention).

Moreover, patients will be given a wristband actigraph which should wear during the whole research period. These devices are capable of detecting the sedentary and activity bouts, as well as the intensity of these last ones, the raw acceleration and the distance walked every day. Besides, actigraphs can also measure the total sleep time, the sleep latency and the awakenings after sleep onset. Thanks to this actigraphy technology, physical functioning and sleep patterns will be effectively daily evaluated.

Thus, by the day of the second evaluation session, we will have already obtained a set of daily measures whose average will serve as a reliable clinical baseline. In this second appointment, as part of the potential biomarkers of chronic pain, we will register the electroencephalography (EEG) of the patients during various conditions (Davis et al., 2017). Firstly, EEG will be assessed during a resting state to capture spontaneous brain

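### Structured side-effect reporting is stated only for the treatment period, so the training stimulation and the post-treatment fortnight have only unstructured contact and the item has no pre-treatment values

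*Combined protocol and SAP*

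**What the plan says.** Section 6.2 describes a daily online survey that starts at the first visit and "continues until fifteen days after the stimulation sessions have finished". On side effects it says: "During treatment period, participants can also report any side effect of stimulation through these questionnaires". The same section treats treatment as a phase of its own: each rated symptom gets one average before treatment, then "other average with measures during the treatment and one last average for post-treatment phase".

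Section 5 places the first possible exposure at the second pre-treatment visit, where the device is handed over: "It is planned to make a training stimulation session during this visit". Section 6.1 repeats this. After treatment, Section 6.1 says, "participants are summoned to other two evaluation sessions with the same structure and assessment tools as in pre-treatment phase". At six months the questionnaires and sensory tests are repeated without the daily scale.

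Objective C (Section 2) is to judge whether the procedures are safe, feasible and acceptable at home. Table 1 lists no safety end point. Section 7 plans a count of dropouts with reasons, as a feasibility index, but no analysis of side effects.

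Section 9 adds that the team will follow patients' progress and be in touch by telephone every day from the pre-treatment phase to the end of the post-treatment phase, partly so that patients can reach them if a problem arises.

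**The concern.** The side-effect item opens when treatment starts and, as written, closes with the last session, although the survey that carries it runs before and after. Three consequences follow.

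- An effect of the training stimulation, or one that appears or persists in the fortnight after the last session, has no structured place to be recorded.
- The item has no pre-treatment values. A patient with chronic pain who ticks headache or dizziness during treatment may have had it all along, and the item cannot show which.
- Nothing says whether the item stays open for a patient who stops stimulation early, the patient in whom it may matter most.

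At stake is Objective C. This item is the only structured symptom-level safety information in the plan, so its window limits what can be concluded about safety at home.

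**Working it through.** The plan states no figure to reproduce. The check is a timeline built from its own day counts, with treatment starting at day 0.

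**Inputs**
- First visit (Section 6.1): "it takes place fifteen days before starting the treatment", so day −15. The diary starts here.
- Second visit (Section 6.1): two weeks later. −15 + 14 = −1, so about day −1. Device handover and training stimulation take place here.
- Treatment (Section 5): "The intervention plan comprises fifteen stimulation sessions applied with a daily frequency", so about 15 days.
- Post-treatment diary (Section 6.2): 15 days.
- Follow-up visit (Section 6.1): six months after treatment ends.

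**Diary days**
- Total: 15 + 15 + 15 = 45.
- Days for which the side-effect item is stated: about 15. 15 / 45 = 33%.
- Days without it: 45 − 15 = 30. 30 / 45 = 67%.

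**Stimulation exposures**
- Scheduled: 15. With training: 15 + 1 = 16, if the training session delivers current, which the plan does not state.
- Inside the window: 15 / 16 = 94%. The one outside it is the first, about one day before the item opens.

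**What covers each phase**

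| Phase | Side-effect item | Daily contact (Section 9) |
|---|---|---|
| Pre-treatment diary, including training visit | not stated | yes, unstructured |
| Treatment, 15 sessions | yes | yes, unstructured |
| Post-treatment diary | not stated | yes, unstructured |
| Six-month visit | not stated | not described |

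**Which symptoms have pre-treatment values**
- Yes: pain intensity, unpleasantness, interference, fatigue and anxiety (daily scales, Section 6.2 and Table 1); mood, fatigue and sleep (HADS, MFIS, PSQI); activity and sleep by actigraphy.
- No: anything that reaches the record only through the side-effect item.

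**The case against.** The strongest reply is that the plan watches patients closely throughout. Section 9 gives daily contact over all three diary phases, including the training day. Researchers are present at the training session, and its lingering effects could be entered about a day later when the item opens. The device stores aborted sessions and faults (Section 5), and reasons for dropout are recorded (Section 7). Worsening of pain, fatigue, mood or sleep can be measured against baseline. The sham arm gives a concurrent comparison during treatment.

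Much of this stands, and it rules out several stronger readings.

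- A reader might infer that harms outside treatment are never collected. Section 9 does not support that: a problem can be reported on any diary day.
- A reader might infer that no patient has a symptom baseline. The main rated symptoms do have one; only the side-effect item does not.
- A reader might count the painful laboratory tests, all outside the treatment period, as a gap in Objective C. They are assessments, not the home intervention, and problems from them are not evidence on its safety.
- A reader might take the introduction's remark that "their clinical improvements last beyond the time stimulation, probably due to solid neuroplastic modifications" as evidence of delayed harm. It concerns benefit. The case for looking after the last session rests on ordinary prudence and on a diary that is running anyway.
- A reader might infer that patients who stop early lose all contact. No text ends their diary or the contact; the plan simply does not say that the item continues.

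The reply does not make the contact a safety record. The documents give it no form, definition or analysis. It may also not be a separate channel, since the survey itself is sent by phone message. Device logs record faults, not symptoms. The sham comparison would rest on about 20% × 120 = 24 patients, and Section 7 does not plan it for side effects.

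**Conclusion.** The point holds in a limited form. Structured side-effect reporting is stated for about 15 of about 45 diary days and only for effects of stimulation. The training stimulation and the post-treatment fortnight are left to unstructured contact, the six-month visit has no described route, and symptoms seen only through this item cannot be compared with pre-treatment values. This weakens the basis for Objective C; it does not leave patients unobserved, and 15 of at most 16 stimulation exposures fall inside the window.

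This assumes that the sentence in Section 6.2 means what it says about timing. The plan does not write that reporting is confined to treatment, but it gives no other period for the item. It also assumes a treatment phase of about 15 days. Whether the training session delivers current is unknown and affects only that part of the point. A wider window alone would not be enough: without a planned summary by arm, the extra data would not serve Objective C.

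**What to change.** 1. **Section 6.2.** Keep the same side-effect item on the existing daily survey from the start of the pre-treatment diary to day 15 after the last scheduled session. Word it as any new or worse symptom. State that it continues for patients who stop stimulation early.
2. **Sections 5 and 6.1.** Ask it once at the end of the training visit and once at the six-month visit.
3. **Section 7.** Add a summary by arm (tDCS, tACS, sham) of effects that are new or worse than in the pre-treatment diary, counted from the training stimulation.
4. **Laboratory tests.** Record any problems from the pain tests separately, and do not count them as evidence on the safety of home stimulation.

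The cost is one item on about 30 diary days that patients already complete, one question at two existing visits, and one table. It needs no new visits or patients. The downside is a slightly longer survey and more unrelated symptoms to tabulate; the pre-treatment values are what allow those to be set aside.
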